### **9.3.3 Removal of Patients from Therapy or Assessment**

A premature discontinuation will occur when a patient who gave voluntary assent and/or whose LAR and/or caregiver signed the ICF ceases participation in the study, regardless of circumstances, before the completion of the study. Patients can be prematurely discontinued from the study for any of the following reasons:

- Screen failure (failure to meet inclusion/exclusion criteria)
- Withdrawal of consent
- Adverse event (AE)
- Lack of efficacy
- Protocol violation
- Non-compliance with investigational product
- Lost to follow-up
- Study terminated by Sponsor
- Site terminated by Sponsor
- Other

All randomized patients who prematurely discontinue from the study, regardless of cause, should be seen for a final assessment at ET (see [Section 9.5.5.6](#) for details on assessments performed at Visit 8/ET). Patients who discontinued from the study and did not return to the site for final assessments must be requested in writing to do so and to return any unused investigational product. A copy of the letter, together with the source documentation, will be kept by the Investigator. The reasons for premature discontinuation from the study will be recorded on the Study Disposition Pages of the eCRF.

All randomized patients must complete Visit 8/ET Visit and return for Visit 9/SFU at the end of the down-taper period. Patients who do not enter the down-taper period must return for Visit 9/SFU approximately 1 week after Visit 8/ET Visit.

### **9.3.4 Patient Replacement Procedures**

Patients in this study who prematurely discontinue treatment will not be replaced.

### **9.3.5 Demographic Considerations**

Efforts will be made to have reasonable representation with respect to gender, race, and ethnicity, reflecting the proportions in the disease population. FRI will monitor enrollment and may instruct the sites accordingly.

## **9.4 TREATMENTS**

Patients meeting the eligibility criteria at Visit 2 (Baseline) will be randomized in a double-blind fashion to 1 of 4 treatment groups: placebo, levomilnacipran 40 mg/day, levomilnacipran 80 mg/day, or fluoxetine 20 mg/day.

### **9.4.1 Treatments Administered**

Investigational product in the form of over-encapsulated capsules and tablets will be packaged in blister cards and provided by FRI. Patients will be supplied with blinded investigational product and will be instructed to take 2 capsules orally each morning (see [Section 9.4.5](#) for details). Confirmation that dosing scheme (including titration and down-taper) and dosing instructions were discussed with the patient and caregiver and that dosing instructions were provided will be recorded in the source documents.

### **9.4.2 Identity of Investigational Products**

Investigational product will be supplied by FRI as capsules containing placebo or levomilnacipran 10 mg capsules, levomilnacipran 20 mg capsules, levomilnacipran 40 mg capsules, fluoxetine 10 mg *capsules*, or fluoxetine 20 mg tablets packaged in blister cards.

The blister cards will contain sufficient numbers of doses for the interval of days between scheduled visits plus additional doses to accommodate visit scheduling.

The blister cards will be labeled with the protocol number, storage information, warning language (viz, “Caution: New Drug—Limited by Federal Law to Investigational Use”), and instructions to take as directed. The Investigator will write the date, visit number, study week, and patient identification (PID) number on the label.

All investigational product will be provided and shipped to the study centers by FRI and must be stored in an appropriate secure area (eg, a locked cabinet in a locked room) at room temperature [REDACTED] and must be protected from light, heat, and moisture.

The Investigator is responsible for recording the receipt and use of all investigational product supplied and for ensuring the supervision of the storage and allocation of these supplies. All unused investigational product must be returned; and, whenever investigational product are returned, unit counts must be performed. All investigational product must be accounted for. At the end of the study, all unused investigational product and empty investigational product packages must be returned to the Sponsor at the address provided in the Study Reference Binder.

### **9.4.3 Method of Assigning Patients to Treatment Groups**

After the patient, LAR, and caregiver provide assent and sign the ICF at Visit 1 (Screening), study personnel will register the patient in the interactive Web response system (IWRS) system, and the system will assign the patient a sequential PID number. The first patient entered into the system at each site will be assigned the first number in the sequence by the system. [REDACTED]

The study center must contact the IWRS at Baseline (Visit 2) and all subsequent study visits in order to obtain the instructions on kit number for the investigational product to be dispensed to the patient at that visit.

A detailed description of IWRS procedures is contained in the IWRS *Site User Guide* that should be stored in the Study Reference Binder.

#### **9.4.4 Selection of Dosages in the Study**

Doses were selected based on the population PK model submitted with NDA 204,168 (Study LVM-MS-01, 2012). To determine the doses for this adolescent study, a simulation was performed to infer adolescent plasma concentrations from adult plasma concentrations for the 120-mg dose. The simulation found that comparable concentrations are expected to be obtained in adolescents at 75% of the adult dose. Levomilnacipran has linear PK in adults and a linear PK profile is expected in children and adolescents. Therefore, plasma concentrations from doses of 30 mg to 90 mg per day in adolescents are expected to correspond to the adult plasma concentrations for the approved adult therapeutic range of 40-120 mg/day.

Levomilnacipran is currently available in 20 mg, 40 mg, 80 mg, and 120 mg capsules. In order to use existing strengths and to have more than 1 arm of levomilnacipran in this fixed-dose study, doses of 40 mg and 80 mg per day have been selected for the adolescent age range. A 10 mg capsule formulation is currently under development for the purpose of titration in this study. The corresponding plasma concentrations of these doses in adolescents are expected to remain within the plasma concentrations associated with the approved therapeutic dose range for adults.

#### **9.4.5 Selection and Timing of Dose for Each Patient**

Patients who meet all eligibility criteria at Screening (Visit 1) and who continue to meet all the eligibility criteria for participation in the study will be assigned a randomization number at Baseline (Visit 2) and dispensed the corresponding blister card containing capsules of double-blind investigational product for Week 1. Patients will begin dosing with double-blind capsules on the next day. Patients will be instructed to take 2 capsules orally as a single dose, once daily at approximately the same time each day (morning dosing recommended), with or without food.

Dosing may be switched from the morning to another time of day if a patient prefers or if tolerability issues arise. However, any switch must allow at least 20 hours between 2 consecutive doses.

[figure not shown]
##### **9.4.5.1 Double-blind Treatment Period**

The titration schedule is as follows:

- Levomilnacipran 40 mg/day treatment group: Days 1-2, 10 mg/day; Days 3-7, 20 mg/day; Week 2 through Week 8, 40 mg/day
- Levomilnacipran 80 mg/day treatment group: Days 1-2, 10 mg/day; Days 3-4, 20 mg/day; Days 5-7, 40 mg/day; Week 2 through Week 8, 80 mg/day

- Fluoxetine 20 mg/day (active comparator): Week 1, 10 mg/day; Week 2 through Week 8, 20 mg/day

Patients will be assigned a randomization number at Visit 2 and dispensed the corresponding blister card containing capsules of double-blind investigational product for Week 1. Patients will begin dosing with double-blind capsules on the next morning. Patients will be instructed to take 2 capsules from each column (1 each from Row A and Row B) as a single dose daily each morning with or without food. The double-blind dosing regimen is presented in Table 9.4.5.1–1.

Patients will be instructed to return the blister card with any remaining investigational product, and to return it even if it is empty, preferably at the next study visit. Additional investigational product will be dispensed as per the schedule shown in [Section 2.0](#).

If a patient experiences an AE, the investigational product may be stopped for up to a maximum of 4 consecutive days. The date and reason for missed doses must be recorded on the appropriate page of the eCRF.

#### **9.4.5.2 Double-Blind Down-Taper Period**

All randomized patients who complete the 8-week double-blind treatment period and patients who prematurely discontinue from the study before completing 8 weeks of double-blind treatment should enter the 1-week, double-blind down-taper period unless it is considered not clinically appropriate by the Investigator. The double-blind down-titration regimen is as follows:

- Levomilnacipran 40 mg/day and 80 mg/day treatment groups: Days 1-2, 40 mg/day; Days 3-7, 20 mg/day
- Fluoxetine 20 mg/day: Days 1-7, 10 mg/day

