## **9.0** **INVESTIGATIONAL PLAN**

### **9.1** **OVERALL STUDY DESIGN AND PLAN: DESCRIPTION**

Study LVM-MD-11 will be a randomized, double-blind, placebo- and active-controlled, parallel group, fixed-dose study in adolescent patients, ages 12-17 years. The study will be approximately 10 weeks in duration:

- 1-week screening/washout period
- 8-week double-blind treatment period
- 1-week double-blind down-taper period

The screening/washout period will generally be 1 week ( $\pm$  3 days) prior to Visit 2, but may be extended up to a total of 5 weeks to accommodate prior medication washout or to repeat assessments. Patients will not receive any investigational product during the screening period.

[figure not shown]
Patients who meet the eligibility criteria at Visit 2 (Baseline) will be randomized to 1 of 4 treatment groups: placebo, levomilnacipran 40 mg/day, levomilnacipran 80 mg/day, or fluoxetine 20 mg/day. See [Section 9.4.5](#) for details regarding dose selection and timing.

All randomized patients who complete the 8-week double-blind treatment period and patients who prematurely discontinue from the study before completing 8 weeks of double-blind treatment should enter the 1-week, double-blind down-taper period unless it is considered not clinically appropriate by the Investigator.

All patients must complete Visit 8/Early Termination (ET) Visit and, at the end of the down-taper period, return for Visit 9/Safety Follow-up (SFU) Visit. Patients who do not enter the down-taper period must return for Visit 9/SFU Visit approximately 1 week after Visit 8/ET Visit.

Approximately 544 patients (136 per treatment group) are planned to be randomized in the study.

[Figure 9.1–1](#) provides a schematic of the study design. The Schedule of Evaluations is presented in [Section 2.0](#). Detailed descriptions of each study visit are provided in [Section 9.5.5](#).

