### 9.7.9 Determination of Sample Size

**Original sample size calculation:** The effect size (treatment group difference relative to pooled SD) of 0.36 for both levomilnacipran and fluoxetine is based on a treatment difference of 4 units with a common pooled SD of 11.1 for the primary efficacy parameter, change from baseline to Week 8 in CDRS-R total score. Adjusting for multiple comparisons of 2 levomilnacipran groups with placebo across the primary and secondary endpoints by using the matched parallel gatekeeping procedure, a sample size of 660 patients (165 per treatment group) will be needed to provide 85% power for primary analysis (levomilnacipran vs placebo) and for assay sensitivity analysis (fluoxetine vs placebo) based on an MMRM model using simulation method (Lu, 2012). The simulation assumed a correlation of 0.7 between the repeated measures and a dropout rate of 17% based on historical data in pediatric patients. Following discussions with FDA, the study will be deemed to be successful if at least 1 of 2 levomilnacipran doses (40 mg/day and 80 mg/day) is shown to be statistically significant versus placebo based on the primary efficacy endpoint. Therefore, the study will be powered at 85% based on at least one of the two dose levels achieving statistical significance, which yields a resultant sample size of 520 patients using the same assumptions.

**Sample size recalculation:** Following a blinded interim analysis, the sample size has been re-estimated. The MMRM model is used to estimate the pooled variance for change from baseline in CDRS-R total score at Week 8; it includes pooled study site and week as factors, and baseline CDRS-R total score and baseline value-by-week interaction as covariates.

A total of 421 subjects were included in the ITT analysis. Of these 421 patients, 347 (82.4%) patients have observed data at Week 8, so the estimated dropout rate at Week 8 is 17.6%. Based on the MMRM model, the variance estimate for the change from baseline in CDRS-R total score at Week 8 is 129.53, and the estimated pooled standard deviation is 11.38. Thus, the estimated effect size is 0.35 based on a treatment difference of 4 units and a pooled standard deviation of 11.38.

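### As written, the single levomilnacipran down-taper raises the dose for patients who stop before titration has reached 40 mg/day

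*Protocol*

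**What the plan says.** Protocol Section 9.4.5.1 titrates the three active arms over Week 1:

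- Lower-dose arm: "Levomilnacipran 40 mg/day treatment group: Days 1-2, 10 mg/day; Days 3-7, 20 mg/day; Week 2 through Week 8, 40 mg/day"
- Higher-dose arm: 10 mg on the first two days, 20 mg on the next two and 40 mg on the last three, then 80 mg/day from Week 2
- Active comparator arm: "Fluoxetine 20 mg/day (active comparator): Week 1, 10 mg/day; Week 2 through Week 8, 20 mg/day"

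Section 9.4.5.2 then gives a single levomilnacipran taper: "Levomilnacipran 40 mg/day and 80 mg/day treatment groups: Days 1-2, 40 mg/day; Days 3-7, 20 mg/day". Fluoxetine patients take 10 mg/day for the 7 taper days. Both completers and patients who discontinue early "should enter the 1-week, double-blind down-taper period unless it is considered not clinically appropriate by the Investigator". Section 9.1 repeats this entry rule. Neither section sets a minimum exposure or ties the taper to the dose reached.

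A route without a taper already exists. Section 9.1 states: "Patients who do not enter the down-taper period must return for Visit 9/SFU Visit approximately 1 week after Visit 8/ET Visit". Section 9.3.3 says the same.

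**The concern.** The taper suits a patient who has reached 40 or 80 mg/day. For one who stops while still on 10 or 20 mg/day, its first two days are an increase, to a dose above any the patient has taken. After a Day 1-2 stop it also skips the 20 mg step that titration places before 40 mg. In every such case the taper ends at 20 mg/day, which is no lower than the dose at which the patient stopped.

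The patients concerned are adolescents who have just stopped, possibly because of an adverse event. What is at stake is a short, avoidable exposure in a period meant to reduce dose.

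**Working it through.** The plan states no figure on this point that could be reproduced. The check compares the last titration dose (Section 9.4.5.1) with the first taper dose (Section 9.4.5.2), and then estimates how many patients are affected.

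**Dose steps**

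| Group | Stop on | Last dose | First taper dose | Ratio |
|---|---|---|---|---|
| Levomilnacipran 40 mg | Days 1-2 | 10 | 40 | 4 |
| Levomilnacipran 40 mg | Days 3-7 | 20 | 40 | 2 |
| Levomilnacipran 80 mg | Days 1-2 | 10 | 40 | 4 |
| Levomilnacipran 80 mg | Days 3-4 | 20 | 40 | 2 |
| Levomilnacipran 80 mg | Days 5-7 | 40 | 40 | 1 |
| Fluoxetine | Days 1-7 | 10 | 10 | 1 |

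From Week 2 no arm has an increase (40 to 40, 80 to 40, and 20 to 10 for fluoxetine).

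The taper totals 2 × 40 + 5 × 20 = 180 mg. A patient stopping on Day 1 or 2 has taken 10 or 20 mg in all. The largest prior total among affected patients is 2 × 10 + 5 × 20 = 120 mg (40 mg group, Day 7). Every affected patient would therefore receive more drug in the taper than before it.

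**Affected group-days.** 7 in the 40 mg group + 4 in the 80 mg group = 11. Of these, 4 are four-fold and 7 two-fold. Days 1-4 account for 8 of 11 (73%).

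**Patients affected.** Inputs from Section 9.7.9: 136 per group and 17.6% dropout. Assumptions, since the documents give no Week 1 figure: one-eighth to one-quarter of dropout occurs in Week 1, spread evenly over the 7 days.

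- Dropouts per group: 136 × 0.176 = 23.9. In Week 1: 23.9/8 = 3.0 to 23.9/4 = 6.0.
- Four-fold step: 2 groups × 3.0 × 2/7 = 1.7, to 2 × 6.0 × 2/7 = 3.4.
- Two-fold step: 3.0 × 5/7 + 3.0 × 2/7 = 3.0, to 6.0.
- Total: 4.7 to 9.4 of 2 × 136 = 272 levomilnacipran patients.
- Of these, 40 mg group on Days 5-7: 3.0 × 3/7 = 1.3, to 2.6.

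**What a change can still reach.** Section 9.7.9 reports: "A total of 421 subjects were included in the ITT analysis". At most 544 − 421 = 123 patients remain (123/544 = 22.6%). This is an upper bound, because others may already have been randomized. Scaled total: 4.7 × 0.226 = 1.1 to 9.4 × 0.226 = 2.1. Scaled four-fold: 0.4 to 0.8.

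The 17.6% comes from ITT patients, who have at least one postbaseline score, so it can miss the very earliest stoppers.

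**The case against.** The strongest reply is that the opt-out already covers this. Entry is recommended, not mandatory, and a patient with a few days at 10 or 20 mg/day is an obvious candidate for skipping the taper. On Days 1-4 the study day alone shows that any levomilnacipran patient is on 10 or 20 mg/day. Even on Days 5-7 the Investigator can see that the dose may be only 20 mg/day. This stands in part: if Investigators always opt out, the number affected is near 0. But the clause gives no criterion for stops during titration and leaves entry as the default. On Days 5-7 whether the taper is an increase depends on the blinded arm (20 or 40 mg/day).

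Second, a rule may sit in text not available here: Table 9.4.5.1-1, the redacted Early Termination visit description, or the IWRS instructions. That cannot be excluded. Nothing visible contradicts the rule in Section 9.4.5.2.

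Third, taper supplies may be dispensed only at a visit, so a direct 10-to-40 step would need an unscheduled visit around Days 1-2. This weakens the even-spread assumption. A later visit does not remove the problem: the patient would then restart, after days off drug, at a dose above any taken before.

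Fourth, the consequence is small. 40 mg/day is the lower target dose and lies within the 30 to 90 mg/day that Section 9.4.4 expects to match approved adult exposure. The 20-to-40 step is itself a scheduled titration step. This is accepted and sets the severity.

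**Conclusion.** The concern holds as a minor design point. The dose steps follow directly from the two schedules and need no assumption: four-fold after a Day 1-2 stop; two-fold after a Day 3-7 stop (40 mg group) or a Day 3-4 stop (80 mg group). Patients in the 80 mg group stopping on Days 5-7, and fluoxetine patients, have no increase.

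The counts do rest on assumption: about 5 to 9 levomilnacipran patients over the whole trial before any opt-out, of whom about 2 to 3 have the four-fold step and 3 to 6 the two-fold step. About 1 to 3 fall on Days 5-7, where the study day does not reveal the dose. A change now would reach about 1 to 2 affected patients, fewer than 1 of them with the four-fold step. Efficacy analyses are unaffected. Confidence is medium because of the unseen dosing table and visit text.

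**What to change.** Add one sentence to Section 9.4.5.2: patients in any arm who discontinue before starting Week 2 dosing do not enter the down-taper, but complete Visit 8/ET and return for Visit 9/SFU about 1 week later. Applying it to all arms keeps the blind. An IWRS block is optional. If the dosing table or Early Termination text already holds such a rule, repeat it in Section 9.4.5.2.

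The cost is that some patients with no dose increase lose a taper. On the same assumptions, over the whole trial, these are about 1 to 3 patients in the 80 mg group stopping on Days 5-7 (3.0 × 3/7 = 1.3 to 2.6, after at most 3 days at 40 mg/day) and about 3 to 6 fluoxetine patients stopping in Week 1.

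If losing the Day 5-7 taper is not acceptable, use a Day 1-4 cut-off in all arms. It removes every four-fold step and 8 of the 11 affected group-days. Only about 2 to 3 fluoxetine patients (3.0 × 4/7 = 1.7 to 3.4) then lose a taper, and the 40 mg group's Day 5-7 stops remain under the opt-out.

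The sentence belongs in the next amendment. The number of patients it can still reach does not justify an amendment of its own.

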#### **9.4.6 Blinding**

A list of patient randomization codes will be generated by Statistical Programming at FRI and implemented by the IWRS vendor (an electronic version will be stored on a secure server). This list will identify each patient by randomization number and include the patient's corresponding treatment assignment.

#### **9.4.7 Unblinding**

Any unblinding at the study center level should be done only in an emergency that requires for the investigational product to be identified for the medical management of the patient. The Investigator must notify the Study Physician immediately (see [Appendix II](#)) and a full written explanation must be provided if the blind is broken. Before the investigational product is unblinded, every attempt should be made to discuss the case with the Study Physician. Breaking the code at the study center will immediately disqualify the patient from further participation in the study.

Treatment codes may be broken by Global Drug Safety at FRI for regulatory reporting purposes. In such cases, the study staff will be kept blinded and the patient will not need to be disqualified from the study.

In an emergency, the Investigator can obtain the treatment assignment of any patient at his/her study center through the IWRS. In an emergency, the Investigator should access the IWRS to break the blind.

#### **9.4.8 Prior and Concomitant Therapy**

A list of concomitant medications that are allowed and not allowed for either episodic or chronic use is provided in [Appendix III](#). Medication history (psychotropic medication history during the previous 5 years and all other medications during the past 12 months) will be recorded at Screening (Visit 1) in the eCRF. Thereafter, any changes in concomitant medications or new medications added will be recorded in the eCRF.

#### **9.4.9 Monitoring Treatment Compliance**

Investigational product compliance during any treatment period will be closely monitored by counting the number of capsules dispensed and returned. Before new investigational product is dispensed at each visit, every effort will be made to collect all unused investigational product. Patients who do not take investigational product for 5 or more consecutive days, or consistently demonstrate poor compliance (< 80% or > 120% in 2 consecutive visit intervals, measured by capsule count) should be considered for study discontinuation. Investigators should consult with the Study Physician before discontinuing a patient due to poor compliance.

#### **9.4.10 Treatment After Discontinuation**

Patients whose MDD symptoms worsen or are determined by the Investigator to be inadequately controlled before completing the double-blind treatment period are allowed to discontinue investigational product and start appropriate treatment at the Investigator's discretion. This new treatment will not be provided by FRI. Patients who initiate a new treatment for MDD must be discontinued from the study.

